#### **3.3.2** Control Group(s)

Not applicable.

#### **3.3.3 Target Parameters**

The following measurements and assessments are requested to be carried out, grouped by the different target parameters:

Immunogenicity

FVIII inhibitor screen

**Prophylactic Treatment** 

Frequency of spontaneous breakthrough bleeds under three times weekly or every other day prophylactic treatment, and in case of surgical prophylaxis

Efficacy

Efficacy assessment at the end of each BE (based on the efficacy scale described in Section 7.2.2.2)

Recovery Investigation

*In vivo* recovery (calculated from the FVIII plasma levels before infusion and the peak level obtained from the 15 minutes and 1 hour post-infusion samples)

Safety

Vital signs (blood pressure, heart rate, respiratory rate and body temperature)

Safety laboratory parameters (red blood cell [RBC] count, white blood cell [WBC] count, haemoglobin, haematocrit, platelet count, alanine amino transferase [ALT], aspartate transaminase [AST], serum creatinine)

Tolerability (occurrence of any AE will be monitored throughout the study)

## **4 STUDY POPULATION**

## 4.1 **Population Base**

Male patients (mainly new-borns or infants, although no age limitation is given) with severe Haemophilia A (FVIII:C < 1%), without any previous FVIII concentrate treatment or any previous treatment with other FVIII-containing blood products will be enrolled into the study.

In total, 100 PUPs will be enrolled by approximately 40 centres from around the world.

## 4.1.1 Inclusion Criteria

In order to qualify for study enrolment, the following criteria must be fulfilled before study entry:

- 1. Male patients
- 2. Severe Haemophilia A (FVIII:C < 1%)
- 3. No previous treatment with FVIII concentrates or other blood products containing FVIII
- 4. Voluntarily given, fully informed written and signed consent given before any studyrelated procedures are conducted (obtained from the patient's parent(s)/legal guardian(s))

## 4.1.2 Exclusion Criteria

Patients will not be included if any of the following exclusion criteria are met:

- 1. Diagnosis of a coagulation disorder other than Haemophilia A
- Severe liver or kidney disease (ALT or AST levels >5 times of upper limit of normal (ULN), creatinine >120 μmol/L)
- 3. Concomitant treatment with any systemic immunosuppressive drug
- 4. Participation in another interventional clinical study currently or during the past 4 weeks

## 4.2 **Prior and Concomitant Therapy**

As this study is conducted in PUPs, patients should not have received prior treatment with FVIII concentrates as per exclusion criterion.

## 4.2.1 Permitted Concomitant Therapy

Concomitant administration of therapies not interfering with the objectives of the study is permitted. Details of any concomitant therapies must be recorded in the Case Report Form (CRF).

Vaccinations are permitted prior and during the study, and immunisations should be given as recommended by the country standards. However – once treatment with IMP has started – vaccinations are recommended to be done after the 20th ED. Additionally, a subcutaneous administration on a day without FVIII administration is recommended.

Patients may only receive anti-fibrinolytics if this is medically indicated / standard of care, e.g. in the course of tooth extractions or other surgeries.

## 4.2.2 Forbidden Concomitant Therapy

No FVIII concentrates other than *Human-cl rhFVIII* must be administered (except for emergency situations).

Patients permanently switching to another FVIII product within the study participation period will be assessed as treatment failures in the efficacy analyses. However, there are exceptions to this rule. Patients will hence not be considered treatment failures in the efficacy analyses, if:

- the use of another FVIII concentrate was due to an emergency case (example: accident requiring treatment with FVIII without patient or intensive care unit [ICU] personnel) having access to Investigational Medicinal Product [IMP])
- the IMP was not available for the patient in time (example: patient experiences a severe bleed but does not have enough product available).

The reason for a patient switching to another FVIII product should be clearly documented in the CRF (and patient diary, if appropriate).

Patients may not receive immuno-modulating drugs (other than anti-retroviral chemotherapy), such as alpha-interferon, prednisone (equivalent to >10 mg/day), or similar drugs.

For patients who developed an inhibitor and undergo an immune tolerance induction it is highly recommended not to be vaccinated during the ITI.

## 4.3 Withdrawal and Replacement of Patients

## 4.3.1 Premature Patient Withdrawal

Subjects have the right to withdraw from the study at any time for any reason, without the need to justify. The Investigator also has the right to withdraw subjects in case of AEs, protocol violations, or for administrative reasons. Since an excessive rate of withdrawals can render the study non-interpretable, the unnecessary withdrawal of subjects must be avoided.

The Investigator will obtain all the required withdrawal details and document the reason(s) for discontinuation in the CRF. Should the reason for removal of a subject be an AE, the main specific event or laboratory test will be recorded in the CRF, and the Investigator will make thorough efforts to clearly document the outcome.

In case of a positive FVIII inhibitor but no ITI initiation, the subject has to be withdrawn from the study.

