In case the patient did not require any IMP from screening until the 3-Monthly Follow-Up visits during the first year, the blood sampling (inhibitor screen, safely laboratory) after 3 and 9 months is optional. After 6 and 12 months a sample is mandatory.

ITI Patient Follow-Up:

Patients who develop an - non-transient - inhibitor and do not agree to start an ITI will be withdrawn from the study.

Patients developing an inhibitor and starting ITI will be closely monitored, once their parents / legal guardians have been informed about the ITI treatment details and gave their written consent before ITI initiation. Depending on the development of the inhibitor: a bi-weekly (later on monthly to 3-monthly) inhibitor titre testing is considered appropriate.

Optional epitope mapping can be performed once the inhibitor is detected.

*Optional* RNA expression analysis can be performed alongside the inhibitor testing at initiation of ITI, 2 and 4 weeks after ITI initiation, and then on a monthly basis until month 6. This may give information on motifs predicting success that should be evident in the first 6 months and give mechanistic information on immune-tolerance.

Once the inhibitor is eliminated, a normalised recovery and half-life are expected during the continued ITI. Patient observation including testing visits is recommended according to progress of the ITI. Samples to test the recovery are recommended to be drawn at baseline and 15 minutes post-injection. For the half-life evaluation, the following sampling time points are recommended: baseline, 15 minutes, 3, 6, 9, 12, (24) hours post-injection.

Patients will complete study participation after a complete success of the ITI (inhibitor-free, normalised recovery and half-life), or after a maximum ITI period of 36 months.

Surgical Visits:

Study subjects may undergo surgical interventions during the course of the study. Depending on the type of surgery, subjects may be hospitalised or not (in case of certain minor surgeries with low risk of post-operative bleeding) at the discretion of the Investigator. Details of surgery, *Human-cl rhFVIII* dosing, expected and actual blood loss, concomitant treatment (including need for additional blood transfusions), and lab investigations will be documented, as well as details of hospitalisation (start and end date, regular ward, intensive care unit stay).

Completion Visit:

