## Immune Tolerance Induction (ITI) (if applicable)

Patients who develop a clinically significant and non-transient FVIII inhibitor will be offered to start ITI with the IMP. Inhibitors that 'disappear' without any clinical signs or symptoms, where no FVIII dosing increase was required, and that turn to <0.6 BU within a period of 6 months after first detection are regarded as "transient".

The modified Bonn Protocol for inhibitor elimination is recommended:

- Low responders (<5 Bethesda Units [BU]) should receive 50-100 IU FVIII/kg BW daily or every second day. In case the inhibitor increases to 5 BU or more, the patient should switch to the high responder regimen.
- High responders ( $\geq$ 5 BU) should receive 100-150 IU FVIII/kg BW every 12 hours.

Once the inhibitor is eliminated (<0.6 BU), the FVIII recovery is  $\geq$ 66% of normal (defined as 1 IU FVIII/kg BW raises the plasma FVIII activity by 1.5%), and the half-life of FVIII is at least 6 hours, a continuous reduction of about 10% of the initial ITI dosage should be initiated, until the patient has reached a prophylactic treatment regimen of 30-50 IU FVIII/kg BW every other day.

Any other ITI approach using Human-cl rhFVIII as the selected FVIII concentrate is possible.

All treatment details and the further development of the inhibitor titre need to be documented.

Patients who do not start ITI within one year after inhibitor detection are withdrawn from the study.

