# ITI Patient Follow-Up:

Patients developing an inhibitor and not starting ITI will be withdrawn from the study, once it can be ruled out that the inhibitor is transient / not requiring ITI. Inhibitors that `disappear' without any clinical signs or symptoms, where no FVIII dosing increase was required, and that turn to <0.6 BU within a period of 6 months after first detection are regarded as "transient".

Patients developing an inhibitor and starting ITI will be closely monitored. Depending on the development of the inhibitor level: a bi-weekly (later on monthly to 3-monthly) inhibitor titre testing is considered appropriate. Optional epitope mapping can be performed once the inhibitor is detected (pre-ITI start), as close as possible after the peak inhibitor level, and after inhibitor eradication. These patients' epitope mapping samples optionally taken at screening / prior to the first exposure to FVIII will also be analysed. Optional RNA expression analysis can be performed alongside the inhibitor testing at initiation of ITI, 2 and 4 weeks after ITI initiation, and then on a monthly basis until Month 6. This may give information on motifs that predict success that should be evident in the first 6 months and give mechanistic information on immune-tolerance.

Once the inhibitor is eliminated, a normalised recovery and half-life are expected during the continued ITI. Patient observation visits including inhibitor screen and FVIII measurements are recommended according to progress of the ITI. Samples to test the recovery are recommended to be drawn at baseline and 15 minutes post-injection. For the half-life evaluation, the following sampling time points are recommended: baseline, 15 minutes, 3, 6, 9, 12, 24 hours post-injection. No wash-out period needs to be respected prior to blood sampling; no ITI injection should be skipped prior to or during the half-life evaluation (last blood sampling should be performed before the next regular ITI dose is injected).

Patients will complete study participation after a complete success of the ITI (inhibitor-free, normalised recovery and half-life), and the start of regular prophylactic treatment, or after a maximum ITI period of 36 months.

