# 7.2 Efficacy/Immunogenicity Assessments

## 7.2.1 Assessments for Primary Endpoint

The primary objective is to investigate the immunogenicity of Human-cl rhFVIII.

Inhibitor activity will be determined centrally by the modified Bethesda assay (Nijmegen modification), using congenital FVIII-deficient human plasma spiked with *Human-cl rhFVIII* at the following time points:

- At baseline (Screening Visit)
- Every 3-4 EDs until ED 20
- Every 10-12 EDs or every 3 months  $\pm$  2 weeks (whichever comes first) after ED 20
- At study completion
- Any time in the case of a suspicion of inhibitor development.

In case of a positive inhibitor result, an inhibitor re-testing using a second separately drawn sample should be performed centrally. The definitions for thresholds are  $\geq 0.6$  to < 5 BU for a "low titre" inhibitor and  $\geq 5$  BU for a "high-titre" inhibitor.

Patients who develop a non-transient inhibitor will have an option to start on ITI treatment. Patients developing inhibitors and not starting ITI will be withdrawn from the study. Inhibitors that `disappear' without any clinical signs or symptoms, where no FVIII dosing increase was required, and that turn to <0.6 BU within a period of 6 months after first detection are regarded as "transient", and continue regular treatment within the study until they have reached ED 100 or a maximum period of 5 years..

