3.4 Assessment of Objectives

3.4.1 Immunogenicity

The *primary objective* is to investigate the immunogenicity of Human-cl rhFVIII.

The *primary endpoint* is the incidence of inhibitors within the observation period. For one patient an inhibitor is assessed to be positive if the modified Bethesda assay (Nijmegen modification) results in a titer ≥ 0.6 BU at any time point during the observation period.

Inhibitor activity will be determined centrally at the following time points: At baseline (Screening Visit), every 3-4 EDs until ED 20, every 10-12 EDs or every 3 months \pm 2 weeks after ED 20 (whichever comes first), at study completion; at any time in the case of a suspicion of inhibitor development.

In case of a positive inhibitor result, an inhibitor re-testing using a second separately drawn sample should be performed centrally; the result of the second sample will be taken as the final result for the time point. Low titre inhibitors will be defined as ≥ 0.6 to < 5 BU, high-titre inhibitors will be defined as ≥ 5 BU.

Patients who develop a non-transient inhibitor will have an option to start ITI treatment. Patients developing inhibitors and not starting ITI within one year after inhibitor detection will be

withdrawn from the study. Inhibitors that 'disappear' without any clinical signs or symptoms, where no FVIII dosing increase was required, and that turn back to <0.6 BU within a period of 6 months after first detection are regarded as "transient". Patients who develop such a transient inhibitor will continue regular treatment within the study until they have reached ED 100 or a maximum period of 5 years.

Definition of inhibitor confirmation and time to inhibitor occurrence:

Occurrence of inhibitors:

For these definitions inhibitor titres determined in the central laboratory are considered.

(I1) FVIII:C high titre inhibitor occurrence is confirmed, if

inhibitor level ≥ 5 BU at one time point $t_{1,H}$ and

- inhibitor level confirmed to be ≥ 5 BU at a subsequent* time

point $t_{2,H}$ or

- retest of sample from *any* time point $t_{3,H}$ ($=t_{1,H}, t_{2,H}$ or later) confirmed to be ≥ 5 BU.

* 'Subsequent' in the context of this document always means 'at a later time point' or 'in a later sample', but not necessarily the immediate consecutive visit or sample.

(I2) FVIII:C Inhibitor occurrence in a patient is confirmed, if

- a high titre inhibitor is confirmed according to (I1)

or if

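### The withdrawal rule for inhibitor-positive patients without ITI in Protocol 4.3.1 and 7.2.1 conflicts with the plan's own transience and one-year rules, and an early leaver with a low titre can be positive under the protocol but unconfirmed under the SAP

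*Protocol*

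**What the plan says.** Six places in the two documents deal with withdrawal of an inhibitor-positive patient who does not start ITI.

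- **Protocol 4.3.1**: "In case of a positive FVIII inhibitor but no ITI initiation, the subject has to be withdrawn from the study". It gives no date and no exemption. The same section also says that "the unnecessary withdrawal of subjects must be avoided".
- **Protocol 7.2.1**: "Patients developing inhibitors and not starting ITI will be withdrawn from the study". It then says that patients whose inhibitor proves transient "continue regular treatment within the study until they have reached ED 100 or a maximum period of 5 years".
- **Protocol synopsis, ITI Patient Follow-Up**: patients with a non-transient "inhibitor and do not agree to start an ITI will be withdrawn from the study". It gives no date.
- **Protocol 6.1.2, ITI Patient Follow-Up**: patients who do not start ITI "will be withdrawn from the study, once it can be ruled out that the inhibitor is transient" or does not need ITI.
- **Protocol 5.4**: "Patients who do not start ITI within one year after inhibitor detection are withdrawn from the study". Its offer of ITI is limited to clinically significant, non-transient inhibitors.
- **SAP 3.4.1**: "Patients developing inhibitors and not starting ITI within one year after inhibitor detection will be" withdrawn. It also keeps transient patients on study to ED 100 or 5 years.

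Protocol 5.4, 6.1.2, 7.2.1 and SAP 3.4.1 define a transient inhibitor alike: no clinical signs, no dose increase, and a titre back below 0.6 BU within 6 months of first detection.

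The rules for calling a patient positive also differ. Protocol 3.1.1 requires a positive result and a confirming second, separately drawn sample. The endpoint sentence in SAP 3.4.1 requires a titre of at least 0.6 BU at any time point. SAP definition I2 is stricter for low titres. SAP definition I1, for high titres, needs two results of at least 5 BU.

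**The concern.** Whether an inhibitor is transient is known only afterwards, up to 6 months after detection. A site that opens 4.3.1 to decide on withdrawal finds the least qualified version of the rule and could act before that time has passed. Another site, working from 6.1.2 or 7.2.1, would keep the same boy to ED 100. If the withdrawn boy has fewer than 50 EDs, Protocol 4.3.2 also calls for a replacement.

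Inhibitor incidence is the primary endpoint. A boy removed early with a low titre may leave with two positive results, enough for Protocol 3.1.1 but too few for I2. The SAP then gives two answers. Its endpoint sentence counts him. Under I2 he has no confirmed inhibitor, and the time-to-inhibitor rule censors him at his last test, which is itself positive. He stays in the ITT denominator either way.

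**Working it through.** **Step 1. Where the texts conflict.**

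| Place | Spares or keeps transient patients | Time allowed |
|---|---|---|
| Protocol 4.3.1 | no | none stated |
| Protocol 7.2.1, withdrawal sentence | no | none stated |
| Protocol 7.2.1, transient inhibitors | yes | none stated |
| Protocol synopsis | yes | none stated |
| Protocol 6.1.2 | yes | until transience is ruled out |
| Protocol 5.4 | not in the withdrawal sentence | one year |
| SAP 3.4.1 | yes | one year |

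On transience, 4.3.1 conflicts with the synopsis, 6.1.2, the later part of 7.2.1 and SAP 3.4.1. On timing, it conflicts with the one-year allowance in 5.4 and SAP 3.4.1. Only SAP 3.4.1 holds both parts of the rule in one place.

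**Step 2. Number of positive results needed.**

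- Protocol 3.1.1: 2.
- SAP I1 (high titre): 2.
- SAP I2 (low titre): 3 by any route. These are a first positive, its retest and a later positive; a first positive, a later positive and the retest of the later one; or three positive time points.

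Take a low-titre patient with a positive first sample, a positive second draw and nothing after that:

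- If the second draw is the retest of the first time point, as SAP 3.4.1 treats it, the later positive is missing. I2 is not met.
- If the second draw is instead a later sample, which the SAP footnote on the word subsequent permits, a retest is missing. I2 is not met.
- With one more positive (a later test, or a repeat assay of either sample under the second reading), I2 is met.

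If he leaves before the second draw, he is not positive under Protocol 3.1.1 either, and the two documents do not part on that rule.

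**Step 3. When the third result normally arrives.** With a positive retest in hand, the next scheduled positive completes I2. That test falls 3-4 EDs later (up to ED 20), then 10-12 EDs later or at 3 months ± 2 weeks, whichever is first. Without retests, three quarterly positives (months 0, 3 and 6) complete it by about month 6. The 6-month and one-year rules therefore normally leave room for confirmation. A literal reading of 4.3.1 may not.

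**Step 4. Size.** The documents give no count of such patients, so the effect is shown for one patient per 100. The assumed base rates are rounded from figures in the documents: 26.8% and 44.5% (trial results cited in SAP 2) and about 30% (Protocol 1.1). The SAP names no interval method; Clopper-Pearson is assumed here.

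| All counted | 95% CI | One unconfirmed | 95% CI |
|---|---|---|---|
| 27/100 = 27.0% | 18.6-36.8 | 26/100 = 26.0% | 17.7-35.7 |
| 30/100 = 30.0% | 21.2-40.0 | 29/100 = 29.0% | 20.4-38.9 |
| 45/100 = 45.0% | 35.0-55.3 | 44/100 = 44.0% | 34.1-54.3 |

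Half-widths with all counted: (36.8 − 18.6)/2 = 9.1, (40.0 − 21.2)/2 = 9.4 and (55.3 − 35.0)/2 = 10.15 points.

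Kaplan-Meier: let b of 100 patients be positive, one of them censored at his own positive test after c earlier events, with no other earlier censoring. The estimate is 1 − (1 − b/100) × (100 − c)/(99 − c).

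- b = 30, c = 0: 1 − 0.70 × 100/99 = 29.3%.
- b = 30, c = 29: 1 − 0.70 × 71/70 = 29.0%.
- b = 27: 26.0% to 26.3%.
- b = 45: 44.0% to 44.4%.

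The fall is 0.6 to 1.0 point.

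**The case against.** The strongest reply is that 4.3.1 is shorthand. Not initiating ITI presupposes that ITI was on offer, and 5.4 offers it only for non-transient inhibitors. An undated sentence can be read as subject to the one-year limit in 5.4. Section 7.2.1 uses a similar bare sentence and then states the exemption, and 4.3.1 itself warns against unnecessary withdrawal. This makes the intended meaning fairly clear. It does not change the fact that the section governing withdrawal is mandatory and omits both qualifications.

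A second reply is that confirmation may still come after he leaves. Protocol 7.3.2 makes every inhibitor an SAE. Sections 7.3.1.1 and 7.3.1.6 follow adverse events, including those leading to withdrawal, until resolved or stable. Section 7.3.3 keeps leftover plasma for at least two years after study completion, so a repeat assay may be possible if volume remains. These routes are real, but none is required for I2. The SAP's data review clause speaks of reclassifying low titre as high, not of rescuing an unconfirmed low titre.

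A third reply is that the study is descriptive and that listings of inhibitor results and discontinuations would already reveal such a patient. That is correct, and it limits the weight of the point. A listing does not say how he counts.

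A reader might also infer that all the cited sections contradict 4.3.1 on both date and transience. They do not, as the table in the working shows.

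**Conclusion.** The point holds and is minor. As written, 4.3.1 and the bare sentence in 7.2.1 can remove patients whom the rest of the plan means to keep. For a low-titre patient who leaves between a positive second draw and any further test, the protocol and I2 disagree unless an optional third result is obtained.

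Two stronger inferences are not supported. The first is that such a patient is necessarily lost from the endpoint: a stored-sample assay or a follow-up sample could confirm him, and the SAP endpoint sentence would count him in any case. The second is that reported incidence is materially understated: the number affected is unknown and may be zero, and each case moves crude incidence by 1.0 point per 100 patients and the Kaplan-Meier estimate by 0.6 to 1.0 point. High-titre cases, ITI entrants and patients followed under the 6-month or one-year rules are normally confirmed.

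The sizes assume 100 patients, base rates of 27%, 30% or 45%, exact intervals and, for Kaplan-Meier, no other earlier censoring.

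**What to change.** 1. **Protocol.** Align 4.3.1 and 7.2.1 with SAP 3.4.1, and align the synopsis and 6.1.2 on timing. Only a non-transient inhibitor without ITI should lead to withdrawal, at the latest one year after detection. Patients with a transient inhibitor continue to ED 100 or 5 years.
2. **SAP.** Leave I2 unchanged. In listing 16.2.8.3, flag patients who meet Protocol 3.1.1 but whose observation ended before I2 could be evaluated. Add one sensitivity row to table 14.2.1.1 that counts them as positive.

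The cost is a small wording amendment in four protocol places, one flag and one table row, with no new visit, sample or assay. The amendment would still need the submissions described in Protocol 10.4, across about 40 planned centres and late in the study: Version 05 is dated February 2018 and the planned end is the fourth quarter of 2018. If sites have already acted, the SAP change alone shows whether anyone was affected. If nobody is flagged, the extra row equals the main row.
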